

Sample Size Estimation/Power Analysis:

Version: 6 February 2017 Revised by PR 2019 10

59th Medical Wing Institutional Review Board

A priori power for a repeated measures ANOVA, mixed effects design, was assessed using G*Power Version 3.1.9.2.

(18) Effect size was based on the NPRS-11 detecting a 1SD difference within groups having a 1SD difference for 4 repeated measures. The results indicate that as few as 5 subjects per treatment group, or 10 total subjects, will have a power of 0.92 to detect a difference of 1SD for the NPRS- 11 at alpha = 0.019. However, post-hoc tests of differences among groups and time periods would require a sample size of 13 subjects per group, 26 total subjects, to achieve a power of 0.81 at alpha = 0.048.

However, sample size must also be based on the RPDD analysis. Effect size is determined by the variance explained by the intervention variable, acupuncture, and the residual variance. Power is based on the alternate hypothesis that the intervention coefficient in the regression model is greater than 0. A priori, both of these variances are unknown for this study. Therefore, power and sample size are based on an assumed small effect size of 0.15. Given there are two predictors, time of repeated measure (fixed effect) and nonacupuncture or acupuncture intervention (covariate), a sample size of 43 subjects in the non-acupuncture to acupuncture sequence will have a power of 0.803 to test this hypothesis at alpha = 0.05. If the number of subjects for the non-acupuncture to acupuncture cohort is kept to 13 in conformance with the first part of the analysis, we will have a power of 0.78 to detect a large effect size of 0.50 at an alpha = 0.055.

Statistical Analysis:

Sample means and standard errors of measurement will be calculated for normally distributed interval variables and medians and interquartile ranges (IQR) for non-normally distributed interval variables. Frequency distributions of nominal and ordinal variables will be calculated. For the first analysis, to test the null hypothesis that there are no differences in outcome measure means between the acupuncture and non-acupuncture groups controlling for within- subject variation and to examine interaction effects, we will employ a mixed effects, repeated measures ANOVA linear model with the data collected for both groups in the first 4 visits. For the second analysis, to test the null hypothesis that the intervention coefficient in the regression model is equal to 0, we will employ a repeated measures ANCOVA linear model with the data collected for the non-acupuncture and acupuncture in 5 visits. Multiple comparison tests to investigate post hoc effects, will be corrected by either the Bonferroni or Holm methods to maintain the alpha level of significance at p=0.05. (19,20) [name], Senior Research Biostatistician Subject Matter Expert for Clinical Research Management under contract W911QY-11-D-0065, is the statistical consultant support for this study.

Statistical analysis will be performed with R Version 3.3.2. (21)

19. Abdi H. Bonferroni and Šidák corrections for multiple comparisons. In N.J. Salkind (ed.). Encyclopedia of Measurement and Statistics. 2007; Thousand Oaks, CA: Sage.

20. Holm, S. 1979. A simple sequential rejective multiple test procedure. Scand. J. Statistics, 6:65-70. 21. R Core Team (2014). R: A language and environment for statistical computing. R Foundation for Statistical Computing, Vienna, Austria. URL http://www.R-project.org/. Number of Subjects: # Planned to Enroll # Enrolled # Planned to Complete Study TOTAL Number of Subjects at Nellis AFB 50 0 44 50 Number of Subjects at Scott AF 50 0 44 50 *If one site recruits more than the other, then they will be able to continue recruitment until the accrual ceiling has been reached. 7. STUDY DURATION Duration of Study: Approximate duration of the study: 3 years 8. LOCAL AND EXTERNAL SUPPORT SERVICES Version: 6 February 2017 Revised by PR 2019 11 59th Medical Wing Institutional Review Board research team and will be administering intervention(s). personnel required 9. INTRAMURAL (GME) AND EXTRAMURAL FUNDING SUPPORT Intramural (GME) and Extramural Funding Support: O&M Intramural grant funding from SG5i was approved for \$17,000. 10. DRUGS, BIOLOGICS, DIETARY SUPPLEMENTS, AND MEDICAL DEVICES Does the study plan dictate the use of any of the following? A drug Yes No A biologic Yes No A compound intended to affect structure or any function of the body Yes No Local and External Support Services: None Describe the plan for training personnel who are not part of the Not applicable – no training of non-study A dietary supplement or substance generally recognized as safe that will be used to diagnose, cure, mitigate, treat, or prevent disease

Yes

No

A medical device

Yes

No

10A. List all drugs covered by an Investigational New Drug (IND) from the FDA (approved or submitted)

N/A, an IND has not been submitted to or approved by the FDA 10B. List all FDA approved drugs being used in accordance with FDA approved labeling

Name of Drug

Dose(s) directed by protocol

Route(s) of administration

N/A, no FDA approved drugs being used according to the labeling 10C. List all FDA approved drugs used for an unapproved use ("off-label")

N/A, no FDA approved drugs being used "off-label" 10D. List all biologics, compounds and dietary supplements

N/A, no biologics, compounds and dietary supplements 10E. List all devices covered by an Investigational Device Exemption (IDE) from the FDA (approved or submitted)

N/A, an IDE has not been submitted to or approved by the FDA 10F. List all FDA approved devices used for an unapproved use ("off-label")

N/A, no FDA approved devices being used "off-label" 10G. List all unapproved devices.

N/A, no unapproved devices 10H. Device Storage Location(s):

Is this research an "applicable clinical trial" which must be registered on ClinicalTrials.gov? Yes, Local Investigator is responsible for registering the trial. NCT02929589

Use of a placebo in place of standard therapy:

Is a placebo being used in place of standard therapy?

No

Yes

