o We will ask if their expectations were met or changed regarding acupuncture's effectiveness for plantar fasciitis.

• Group 2:

o Self-reported pain severity (0 for no pain to 10 being the worst pain)

* CROSSOVER: At Visit 5 (final visit), those in the non-acupuncture group still experiencing pain and symptoms will be rolled into the acupuncture treatment arm of the study as outlined above. If the acupuncture group is still having pain they will be referred back to their primary care manager for further evaluation.

Those subjects in Group 2 (non-acupuncture) that cannot make it to a follow up visit, may have their follow up visits via telephone.

Acupuncture:

This type of Acupuncture for this indication is routinely done as part of standard of care in our Family Medicine and acupuncture clinics in conjunction with a standard of care prescribed exercise program and as a stand-alone therapy. The Research Coordinator will record the name of the investigator performing the acupuncture and also the number of acupuncture needles placed for each treatment.

Acupuncture treatments will be utilizing the KB-2 points with manual manipulation accomplished by vigorously running the acupuncturists thumb nail up and down the handle until a perceived sensation change is noted in the patient's foot. A single needle will

be inserted as stated above and if the sensation change is not noted throughout the entire plantar and dorsal surfaces of the foot a second needle will be inserted over the first needle. This needle will be manipulated in the same manner as the first needle. This can be repeated up to a third needle if the desired change in sensation is not noted. No more than 3 KB-2 needles will be placed per leg. The needles will be removed after the treatment is complete, which will last approximately 5-10 minutes (standard care).

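### The crossover figures (43 subjects, power 0.803; 13 subjects, power 0.78) count one independent score per patient, so they do not establish power or sample size for the planned within-patient repeated-measures test, in either direction

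*Combined protocol and SAP*

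**What the plan says.** Section 6, Sample Size Estimation/Power Analysis, says that the sample size must also rest on the regression point displacement analysis of controls who cross over. The effect size is defined by the variance that acupuncture explains and the residual variance. Both are said to be unknown, so "power and sample size are based on an assumed small effect size of 0.15". With two predictors, time and intervention, "a sample size of 43 subjects in the non-acupuncture to acupuncture sequence will have a power of 0.803 to test this hypothesis at alpha" of 0.05. A fallback follows: "If the number of subjects for the non-acupuncture to acupuncture cohort is kept to 13 in conformance with the first part of the analysis", power is given as 0.78 for an effect of 0.50 at alpha 0.055. On direction, "Power is based on the alternate hypothesis that the intervention coefficient in the regression model is greater than 0".

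The analysis itself is set out under Statistical Analysis in the same section: "we will employ a repeated measures ANCOVA linear model with the data collected for the non-acupuncture and acupuncture in 5 visits". Its purpose is "to test the null hypothesis that the intervention coefficient in the regression model is equal to 0". Section 3 supplies the design: controls still in pain at Visit 5 "will be rolled into the acupuncture treatment arm of the study as outlined above". The same patients are therefore scored first without and then with acupuncture.

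For this calculation the plan gives no number of scores per patient and no within-patient correlation. The first analysis, in the same section, is sized explicitly for four repeated measures.

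**The concern.** A power figure should belong to the test that will be run. In the second analysis the acupuncture effect is a contrast inside each patient. Its precision depends on the number of scores before and after crossover, how they are spaced, how strongly a patient's scores correlate, and how much of the contrast is absorbed by the time trend. None of these enters a calculation with 40 residual degrees of freedom for 43 patients. One score per patient cannot show the same patient off and on acupuncture, nor support a predictor for time of repeated measure.

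Only controls with continuing symptoms cross over, so the team will have to judge whether the number it obtains is enough. If 43 is the yardstick, that judgement could go wrong either way: a sufficient cohort could be called underpowered, or an insufficient one called adequate.

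**Working it through.** **Step 1. Reproduce the plan's figures.** Inputs from Section 6: f² = 0.15, N = 43, alpha 0.05; and f² = 0.50, N = 13, alpha 0.055. Two predictors; the coefficient is tested as greater than 0. For one coefficient in an ordinary regression, noncentrality = √(f²·N) and df = N − 2 − 1.

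- N = 43: √(0.15 × 43) = 2.540, df = 40, one-sided critical t = 1.684, power 0.8028 (stated 0.803). N = 42 gives 0.794, so 43 is the smallest N reaching 0.80.
- N = 13: √(0.50 × 13) = 2.550, df = 10, one-sided critical t = 1.754, power 0.783 (stated 0.78).

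Both match. Other readings of the N = 43 case do not: two-sided, the same regression gives 0.698 (55 needed); an omnibus F test with 2 df gives 0.583; 0.15 read as a standardised paired difference gives 0.249.

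**Step 2. Compare with the planned test.** The df of N − 3 counts each patient as one independent observation. The planned model has several scores per patient, with acupuncture varying only within the patient. The arithmetic is right, but for a different model.

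**Step 3. What 43 crossovers could give.** The documents do not fix this, so the following are assumptions:

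- f² = 0.15 is read as an on/off shift δ = 2√0.15 = 0.775 SD.
- The model has an intercept, a linear time trend and an acupuncture indicator.
- Correlation ρ is equal between all visits, from 0 to 0.7.
- There is no patient-to-patient variation in response to acupuncture.

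With V = ρJ + (1 − ρ)I, the per-patient variance v of the acupuncture coefficient is its diagonal entry in (XᵀV⁻¹X)⁻¹. Then dz = δ/√v, noncentrality = dz·√n and df = n − 1. In each layout v equals its value at ρ = 0 times (1 − ρ).

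| Scores per patient (weeks) | ρ | v | dz | Power at 43, one-sided 0.05 | Needed for 0.80, one-sided | Needed, two-sided |
|---|---|---|---|---|---|---|
| Nine: 0, 2, 4, 6, 12 off; 14, 16, 18, 24 on | 0 | 1.688 | 0.596 | 0.986 | 19 | 25 |
| | 0.7 | 0.506 | 1.089 | >0.999 | 7 | 9 |
| Five: 0, 6, 12 off; 18, 24 on | 0 | 3.333 | 0.424 | 0.86 | 36 | 46 |
| | 0.7 | 1.000 | 0.775 | >0.999 | 12 | 16 |
| Five: four off, one on (0, 2, 4, 6; 12) | 0 | 5.300 | 0.336 | 0.70 | 56 | 72 |
| | 0.7 | 1.590 | 0.614 | 0.99 | 18 | 23 |

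For the second layout at ρ = 0, two-sided power with 43 is 0.776. The last layout shows what a single on-acupuncture score would do; it is not a schedule that the protocol states.

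**Step 4. Sensitivity.** If response to acupuncture varies between patients with variance τ², v becomes v + τ². With τ from 0.775 to 1.0 (assumed) and ρ = 0, the two-sided need rises from 25 to 32–38 with nine scores, and from 46 to 54–59 with the second layout.

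**The case against.** The strongest defence is that 0.803 may be a within-patient figure after all. A one-sided paired test with dz = √0.15 = 0.387 gives 0.8033 at N = 43. This stands as a coincidence that cannot be ruled out from that figure alone. But the matching paired test at N = 13 (dz = √0.50, alpha 0.055) gives 0.792, which rounds to 0.79 and not to the stated 0.78, and a paired test has no place for the two predictors that the plan names. The regression fits both figures. Even on the paired reading, neither the number of visits nor the time trend would have been accounted for.

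A second objection is that any replacement figure is the reviewer's own. This also stands. The conversion to 0.775 SD supposes an even split between off and on scores and a total-SD scale, and the plan says that the variances are unknown. The number of scores is unclear too: Statistical Analysis refers to five visits, the procedures table in Section 3 lists seven pain scores and four foot-function forms per participant, and nine is only a reading of the crossover note. The table above shows a spread, not a corrected answer.

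A reader might infer that 43 overstates the need two-fold or more. That holds under the nine-score layout with the assumptions above, but not generally: with five scores and low correlation, 43 can be too few. A reader might also infer that 43 set the trial's size, since 2 × 43 = 86 lies just below the 88 planned completers (44 at each of two sites). The documents do not derive 88 or 100 from it.

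**Conclusion.** The point holds as a mismatch between the sizing model and the planned test. Both crossover power figures are correct for a one-sided regression on independent scores, one per patient, and neither belongs to the repeated measures ANCOVA in Section 6. Under the Step 3 assumptions, one-sided power with 43 crossovers lies anywhere from 0.70 to above 0.99, and the number needed for 80% power anywhere from 56 down to 7. In most of these scenarios 43 is more than enough, but the direction is not settled by the documents. No single corrected figure can be given until the score schedule and a correlation range are stated. The identification of the regression rests on its matching both stated powers; the ranges rest on the assumed shift, linear trend and equal correlation. The randomised comparison is not affected.

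**What to change.** In Sample Size Estimation/Power Analysis, replace the 0.803/43 and 0.78/13 statements with power for the within-patient acupuncture coefficient of the model in Statistical Analysis. State:

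- how many scores per patient enter before and after crossover, and at which weeks;
- a range for the within-patient correlation;
- the effect in score units of the outcome concerned;
- whether the test is one- or two-sided, since the power text gives a direction and the analysis text does not.

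Then give either the number of crossovers needed or the shift that the expected number can detect, across that range. Until this is done, 43 should not be used to judge whether the crossover analysis is adequately powered. If 43 was the basis for the enrolment target, say so and show the step.

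The cost is rewriting one paragraph. No patients, visits or data items change.

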3. RESEARCH DESIGN AND METHODS

All of the below items are research-related unless marked as 'standard of care': Screening Visit:

- Obtain and document signed Informed Consent document and HIPAA Authorization.
- Review past medical history in Armed Forces Health Longitudinal Technology

Application (AHLTA) to verify the inclusion/exclusion criteria including previous encounter, vital signs review, medication list, co-morbidities, demographics, and problems list.

• Record: Date of birth, age, gender, race, ethnicity, last 4 of social security number, name of standard of care medications (over-the-counter and prescription), current email address (to be used for scheduling), height (in inches), weight (in pounds), history of prior foot injury, and note any prior acupuncture received.

• We will ask what the subjects expectations are regarding acupuncture's effectiveness for plantar fasciitis.

• If the subject is an active duty member, we will ask:

o Have you or are you currently on a fitness restriction for plantar fasciitis.

o If so, what are the dates of the restriction.

• There are several standard of care treatments for plantar fasciitis which include physical therapy and a standard of care prescribed home exercise program. We will standardize what patients in this study are receiving by having all subjects follow the standard of care prescribed home exercise program and discontinue any formal physical therapy when entering this study (regular physical activity such as exercise is allowed).

Visit 1-Day 1 (may be same day as screening visit):

• Subjects will be given a study diary to document the number of times they performed the standard of care prescribed home exercise program. Subjects will be advised to complete the stretching exercises daily and the strengthening exercises every other day.

• Administer the Foot Function Index-Revised short form (FFI-R short)

• Subjects will be randomized into one of two groups and the intervention will be performed:

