Acupuncture treatments will be as defined: The KB-2 points (see figure 1 below) will be used as the treatment points. KB-2 are generally not defined specific points, but are referred to the placement of the needle into the lateral leg and advanced through the interosseous membrane. The initial KB-2 point will be placed in the lower 1/3 of the leg above the lateral malleolus. The second needle will be placed in the middle 1/3 only if pain is still present after insertion and stimulation of the first needle. The third needle will be placed in the upper 1/3 only if pain is still present after insertion and stimulation of the first 2 needles. This study will follow all FDA requirements for the safe use of these devices. The acupuncture being performed in this study is a standard acupuncture technique for the treatment of plantar fasciitis. The physicians performing the treatment are trained in this acupuncture technique. As such, all physicians trained in this procedure will be able to perform the acupuncture for treatment of research subjects. The Food and Drug Administration (FDA) regulates acupuncture needles as a class II medical device, because

they are intended for use in the cure, mitigation, treatment, or prevention of disease in man or are intended to affect the structure or function of the body of man. The FDA regulates the acupuncture needles (see 21 CFR 880.5580). The needles being used are Hwato 0.30X100mm Acupuncture needles (see figures 2-3 above), which are exempt from premarket notification by the FDA for use in acupuncture and will be used in accordance with their FDA approved labeling.

Home Therapy:

Version: 6 February 2017 Revised by PR 2019 5

59th Medical Wing Institutional Review Board

No acupuncture will be performed on this group for treatment of plantar fasciosis. This group will only receive the standard of care prescribed home exercise regimen at the initial visit and have the exercises demonstrated to them. These subjects will follow-up at 2 weeks and 4 weeks and education and demonstration will be performed again with these patients at subsequent visits. a. Interventions and Observations:

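### No site term is specified in the model comparing group means across two recruiting bases: a modest, avoidable loss of precision

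*Combined protocol and SAP*

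**What the plan says.** - **Sites.** The Number of Subjects table (section 6) reads "Number of Subjects at Nellis AFB 50 0 44 50 Number of Subjects at Scott AF 50 0 44 50", that is, 50 to enroll and 44 to complete at each base. The note beneath it says "If one site recruits more than the other, then they will be able to continue recruitment until the accrual ceiling has been reached". Section 3b names a family medicine residency clinic at Scott and the military treatment facility at Nellis.
- **Randomisation.** Section 3, Visit 1, says "Subjects will be randomized into one of two groups and the intervention will be performed". No ratio, blocking or stratification by site is stated.
- **First analysis.** Statistical Analysis (section 6) says "we will employ a mixed effects, repeated measures ANOVA linear model with the data collected for both groups in the first 4 visits". The null hypothesis concerns differences in outcome means between the groups, "controlling for within- subject variation and to examine interaction effects". The interactions are not named, and neither is site.
- **Second analysis.** The sample size text gives the crossover model two predictors, time and intervention.
- **Practitioners.** Under Acupuncture (section 3), "all physicians trained in this procedure will be able to perform the acupuncture".
- **Data handling.** Each site's data are de-identified before analysis (sections 3f and 4). Nothing says that site is kept as an analysis variable.

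**The concern.** Site is an obvious design factor here, and the plan handles it neither in the allocation nor in the analysis. The stated test of group means is a between-subject comparison. If patients at one base tend to have higher scores than at the other, that stable difference sits in the between-subject error. Controlling for within-subject variation does not remove it.

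Two consequences follow, depending on how allocation is actually done:
- **Arms balanced within site.** The estimate is free of the site difference, but its standard error is not, so the test is conservative.
- **Allocation ignores site.** The arms can differ in site mix by chance, and the resulting error is not adjusted for.

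Either way some power is lost. Leaving the term unspecified also leaves a modelling choice open until the data are in hand.

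**Working it through.** **Inputs.** From section 6: two sites, 44 completers at each, 88 in total. A 1:1 ratio, giving 44 per group, is inferred from the equal group sizes in the power text. The site difference D (in within-site SD of the patient-level outcome) and the 0.6 SD treatment effect used below are assumptions; the documents give neither.

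**The plan's own figure.** Section 6 states power 0.81 for 13 per group, a 1 SD difference and alpha 0.048. A one-sided two-sample calculation gives 0.812 (normal approximation) or 0.791 (noncentral t); two-sided noncentral t gives 0.680. The stated figure is thus reproduced to within 2 points as a one-sided result. A missing site term does not make it wrong.

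**Variance left in.** With a share p of patients from one site, omitting site multiplies the between-subject variance by V = 1 + p(1−p)D². At p = 0.5 this is 1 + D²/4, and the fraction due to site is (D²/4)/(1 + D²/4).

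**Size of the unadjusted test if arms are balanced within site.** The estimate varies with variance 1 but is judged against V, so the actual size is 2[1 − Φ(1.96√V)].

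**Power without a site term.** Two-sided noncentral t, alpha 0.05, 86 df, noncentrality 0.6 × √(44/2) / √V.

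| D (SD) | V | Variance due to site | Size if balanced within site | Power, 44 per group, 0.6 SD effect |
|---|---|---|---|---|
| 0 | 1.0000 | 0% | 0.050 | 0.795 |
| 0.3 | 1.0225 | 2.2% | 0.047 | 0.786 |
| 0.5 | 1.0625 | 5.9% | 0.043 | 0.770 |
| 0.8 | 1.1600 | 13.8% | 0.035 | 0.734 |

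**Chance imbalance.** With 88 completers allocated 44:44 without regard to site, the share from one base differs between arms by about 8 percentage points on average. The 95th percentile is about 23 points at a 50/50 site split. With D = 0.5, 23 points moves the estimated effect by 0.23 × 0.5 ≈ 0.11 SD, against a standard error of √(2/44) ≈ 0.21 SD. This is the same variance as in the table, seen in a single trial; it is not a further loss.

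**Simulation of the group test** (70/30 site split, one value per patient):
- Unstratified allocation, no site term: type I error 0.046 to 0.050 across 26 and 88 patients and D of 0.5 and 1.0.
- Stratified allocation, no site term, D = 1.0: type I error 0.027 (26 patients) and 0.033 (88 patients).
- Gain from a site term, 88 patients, unstratified, 0.6 SD effect: power 0.775 to 0.793 at D = 0.5, and 0.718 to 0.800 at D = 1.0.
- With 26 patients, unstratified, 1 SD effect and D = 0.5 there is no gain (0.663 without, 0.660 with).

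**Where the term has no effect.** In a simulated repeated-measures dataset (88 patients, four visits, complete data, random intercept), adding site left every group-by-time coefficient and standard error unchanged. Only the between-group level term moved, its standard error going from 0.221 to 0.210. In a simulated crossover cohort of 43 patients, the intervention coefficient (−0.2755) and its standard error (0.0710) were the same with and without site.

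**The case against.** The strongest reply is that little is at stake. The hypothesis concerns improvement acutely and over time, which is most naturally a group-by-time contrast, and a constant site difference drops out of that. At the plan's own 1 SD effect with 44 per group, two-sided power is 0.996 with no site difference, 0.994 at 0.5 SD and 0.991 at 0.8 SD. No document reports that the bases differ at all. All of this stands and sets the priority low. It does not remove the point, because the null hypothesis in section 6 is about group means, and a true effect smaller than 1 SD would lose more.

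A reader might also infer more than the documents support:
- **That unequal recruitment is the cause.** Unequal site totals do not unbalance the arms, and p(1−p) is largest at 50/50. At D = 0.5, V is 1.0625 at 50/50 and 1.0525 at 70/30, so the over-recruitment rule slightly reduces the loss.
- **That the model contains only group, time and their interaction.** No formula is printed, and the two named predictors belong to the second analysis. What can be said is that no site term is specified.
- **That practitioners and coordinators differ by base.** This is likely, but not stated.
- **That the crossover model needs the same term.** It follows the same patients from one condition to the other, so a stable site difference cancels.

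**Conclusion.** The point holds as a minor gap in precision and pre-specification, confined to the between-group level test in the first analysis. For site differences of 0.3 to 0.8 SD the loss is about 1 to 6 points of power at a 0.6 SD effect (0.795 to 0.786 at one end, 0.734 at the other). Those figures rest on an assumed site difference, an assumed effect, 1:1 allocation and a single value per patient. The conservative test sizes also require within-site balance, which the documents do not state.

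It would be tempting to read this as a threat to validity. It is not: false positives are not inflated, the randomised comparison is not biased, and none of the stated sample size or power figures is wrong because of it.

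**What to change.** - In Statistical Analysis, name site (Scott, Nellis) as a fixed effect in the first repeated-measures model.
- Keep a site indicator in the de-identified analysis dataset.
- State whether randomisation is stratified by site. The site term is usable either way.
- Show the treatment effect by site descriptively, without a formal test.

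No site term is needed in the crossover model. The cost is a sentence or two of wording and one degree of freedom (86 to 85 with 88 completers in the simple two-group comparison). No new data are needed, because each patient's base is known at enrollment. The change is best made before outcome data are reviewed.
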